16.4.1.3. Long-Term Follow-Up Phase

Study Phase	Date range
Long-Term Follow-Up	Date > max (Last CAB/RPV Injection Date, Last Oral Bridging End Date)

- Date = Assessment/Start Date
- Only applicable to subjects who have received at least 1 injection
- LTFU phase is not applicable for those who transition to commercial supply. Last oral Bridging may be CAB/RPV or SOC ART Oral Bridging where CAB/RPV is not available due to COVID-19.

Note that the long-term follow-up Phase and Maintenance/Extension Phases are not necessarily mutually exclusive and are to be defined with separate Phase variables in the datasets.

16.4.1.4. Study Phases for Concomitant medication/ART

Study Phase	Date range
Prior	Medication Taken < Maintenance Treatment Start Date
Maintenance ^[a]	
Q2M Arm (OLI and D2I):
 
For participants continuing into Extension Phase: OLI: Maintenance Treatment Start Date ≤ Medication Taken < Date of Nominal Month 14 Injection Visit D2I: Maintenance Treatment Start Date ≤ Medication Taken < Date of Nominal Month 13 Injection Visit
 
For participants not continuing into Extension Phase: Maintenance Treatment Start Date ≤ Medication Taken < LTFU ART Start Date (if applicable)
 
Note: LTFU ART start date is not applicable for those who transition to commercial supply.
 <hr/> 
BIK Arm:
 
For participants continuing into Extension Phase: Maintenance Treatment Start Date ≤ Medication Taken < min (Start Date of Extension Phase CAB/RPV oral lead-in, Date of first Extension Phase CAB/RPV injection)
 
For participants not continuing into Extension Phase:
 
Medication Taken ≥ Maintenance Treatment Start Date

Extension ^[b]	
Participants continuing maintenance CAB LA + RPV LA into Extension Phase
 
OLI: Date of Nominal Month 14 Injection Visit ≤ Medication Taken < LTFU ART Start Date (if applicable) D2I: Date of Nominal Month 13 Injection Visit ≤ Medication Taken < LTFU ART Start Date (if applicable)
 
Participants Switching from Maintenance BIK Arm to CAB LA + RPV LA:
 
min (Start Date of Extension Phase CAB/RPV oral lead-in, Date of first Extension Phase CAB/RPV injection) ≤ Medication Taken < LTFU ART Start Date (if applicable)
 
Note: LTFU ART start date is not applicable for those who transition to commercial supply.

Study Phase	Date range
Long-Term Follow-Up	
For participants who received at least one CAB and/or RPV Injection:
 
Medication Taken ≥ LTFU ART Start Date
 
Note: LTFU phase is not applicable for those who transition to commercial supply.


[a]: ART stopped on the start date of Maintenance Treatment will be considered a prior medication and will not be considered concomitant during the Maintenance Phase. If the stop date of ART medication is completely missing and this medication is recorded in eCRF as prior, it will be considered a prior medication and will not be considered concomitant during the Maintenance phase.
 
[b]: ART stopped on the start date of Extension Phase IP will not be assigned to the Extension Phase.
	

If a partial date for medication/ART is recorded in the eCRF, the following convention will be used to assign the medication:

- if the partial date is a start date, a '01' will be used for missing days and 'Jan' will be used for missing months;
- if the partial date is a stop date, a '28/29/30/31' will be used for the missing day (dependent on the month and year) and 'Dec' will be used for the missing month; for medications recorded separately in the eCRF as prior ART, the earlier of this imputed date or the day before IP start will be used.

16.4.2. Study Periods

Certain displays will be produced for data collected during the oral-lead-in. These period variables are defined in the tables below and will be reflected in the datasets with separate variables.

16.4.2.1. Oral Lead-in Period for AE Data

Study Period	Date range
Maintenance Phase Oral Lead-in	
Q2M OLI subjects only:
 
For participants receiving at least one Injection: Maintenance Treatment Start Date ≤ Date < Date of First Maintenance Phase CAB/RPV Injection
 
For participants withdrawing prior to first Injection: Date ≥ Maintenance Treatment Start Date
 
Note that the oral lead-in period is only applicable to the participants who received at least one dose of study treatment during the oral lead-in period in the study. Oral lead-in period is within the maintenance phase.

Extension Phase Oral Lead-in	
Switch Q2M OLI subjects only:
 
For participants receiving at least one Extension Phase Injection: Extension Oral CAB/RPV Start Date ≤ Date < Date of First Extension Phase CAB/RP injection
 
For participants withdrawing prior to first Extension Phase Injection: Date ≥ Extension Phase Oral CAB/RPV Start Date

16.4.2.2. Oral Lead-in Period for Lab assessments

Study Period	Date range
Maintenance Phase Oral Lead-in	
Q2M OLI subjects only:
 
For participants receiving at least one Injection: Maintenance Treatment Start Date < Date ≤ Date of First Maintenance Phase CAB/RPV Injection
 
For participants withdrawing prior to first Injection: Date > Maintenance Treatment Start Date
 
Note that the oral lead-in period is only applicable to the participants who received at least one dose of study treatment during the oral lead-in period in the study. Oral lead-in period is within the maintenance phase.

Extension Phase Oral Lead-in	
Switch Q2M OLI subjects only:
 
For participants receiving at least one Extension Phase Injection: Extension Oral CAB/RPV Start Date < Date ≤ Date of First Extension Phase CAB/RP injection
 
For participants withdrawing prior to first Extension Phase Injection: Date > Extension Oral CAB/RPV Start Date

------------------------------	--

16.4.3. Treatment State

Within each treatment study phase (i.e. Maintenance, and Extension—based on assignment of study phase described in Section 16.4.1), only those assessments which occur within the ranges shown below will be considered ‘on-treatment’ for the given phase. Note “on-treatment” criteria will not be implemented for adverse event summaries.

Table 7 Treatment State within Study Phases

Study Phase ^a	Treatment State	Date Range
Screen	Pre-treatment	All assessments/events within Phase
Maintenance	On-treatment	Q2M Arm: Date ≤ max (Date of Last Injection Dose + 67, Date of Last Oral Dose + 1)
		BIK Arm: Date ≤ Maintenance ART Stop Date + 1
	Post-treatment	Q2M Arm: Date > max (Date of Last Injection Dose + 67, Date of Last Oral Dose + 1)
		BIK Arm: Date > Maintenance ART Stop Date + 1
Extension	On-treatment	Date ≤ max (Date of Last IP Injection Dose + 67, Date of Last Oral Dose + 1)
	Post-treatment	Date > max (Date of Last IP Injection Dose + 67, Date of Last Oral Dose + 1)
Long-Term Follow-up	On-treatment	Date ≤ min (LTFU ART start date, max (Date of Last IP Injection Date + 67, Date of Last Oral Dose + 1))
	Post-treatment	Date > min (LTFU ART start date, max (Date of Last IP Injection Date + 67, Date of Last Oral Dose + 1))
Note: 
 Treatment State is determined after data has been assigned to the study Phases as defined in Section 16.4.1 		

- The upper bound with last IP injection / last oral dose /Maintenance ART Stop Date should only be applied to participants who permanently discontinue from study treatment
- Date = Assessment/Start Date.
- Last oral dose may be CAB/RPV or SOC ART Oral Bridging where CAB/RPV is not available due to COVID-19.

16.4.4. Combining Treatment Phases and States

On-treatment and Post-treatment assessments and events will be classified as occurring during the Maintenance Phase, Extension, or Long-term follow up Phase.

16.5. Appendix 5: Data Display Standards & Handling Conventions

16.5.1. Reporting Process

Software	

 The currently supported versions of SAS software or R/RStudio will be used. The specific versions of SAS or R packages used to generate the analyses will be detailed in the ADRG. 	
Reporting Area	
HARP Server	: us1salx00259
HARP Compound	: \ARPROD\GSK1265744\mid213500
Analysis Datasets	

 Analysis datasets will be created according to CDISC standards (SDTM IG Version 3.2 & ADaM IG Version 1.2). For creation of ADaM datasets (ADCM/ADAE), the same version of dictionary datasets will be implemented for conversion from SI to SDTM. 	
Generation of RTF Files	

 RTF files will be generated for reporting efforts described in the RAP. 	

16.5.2. Reporting Standards

General

 The current GSK Statistical Display Standards in the GSK Standards Library (IDSL) will be applied for reporting, unless otherwise stated (Library Location: https://spope.gsk.com/sites/IDSLLibrary/SitePages/Home.aspx): 
 4.03 to 4.23: General Principles 5.01 to 5.08: Principles Related to Data Listings 6.01 to 6.11: Principles Related to Summary Tables 7.01 to 7.13: Principles Related to Graphics Do not include participant level listings in the main body of the GSK Clinical Study Report. All participant level listings should be located in the modular appendices as ICH or non-ICH listings
Formats

 GSK Statistical Display Principles (5.03 & 6.06.3) for decimal places (DP's) will be adopted for reporting of data based on the raw data collected, unless otherwise stated. Numeric data will be reported at the precision collected on the eCRF. The reported precision from non eCRF sources will follow the GSK Standard Statistical Display Principles but may be adjusted to a clinically interpretable number of DP's.
Planned and Actual Time

 Reporting for tables, figures and formal statistical analyses: 
 Planned time relative to dosing will be used in figures, summaries, statistical analyses and calculation of any derived parameters, unless otherwise stated. The impact of any major deviation from the planned assessment times and/or scheduled visit days on the analyses and interpretation of the results will be assessed as appropriate. Reporting for Data Listings:

 • If space permits, planned and actual time relative to study drug dosing will be shown in listings (Refer to GSK Standard Statistical Display Principle 5.05.1). • Unscheduled or unplanned readings will be presented within the participant's listings. 	
Unscheduled Visits	

 • Unscheduled visits will be slotted to analysis time points as per Section 16.3. • However, data summaries will only report visits that are planned assessment time points for each parameter (according to the Time and Events table). • Assessments at unscheduled visits will be included for 'any time On-treatment' time points and in data listings, as well any algorithms that make use of additional data (e.g., Snapshot and PDVF identification). • All unscheduled visits will be included in listings. 	
Descriptive Summary Statistics	
Continuous Data	Refer to GSK Standard Statistical Display Principle 6.06.1
Categorical Data	N, n, frequency, %
Graphical Displays	

 • Refer to GSK Standard Statistical Display Principals 7.01 to 7.13. 	

16.6. Appendix 6: Derived and Transformed Data

16.6.1. General

Multiple Measurements at One Analysis Time Point
 
 • If after window assignment there are multiple valid assessments of a parameter within the same window, then the following hierarchy will be used to determine the value to be used for summary statistics of observed values: 
 ○ the assessment closest to the window target Study Day (or target Injection Study Day if injection study day is used for assessment window slotting); ○ if there are multiple assessments equidistant from the target Study Day or target Injection Study Day, then for continuous variables the mean of these values will be used and for categorical variables the worse assessment. For HIV-1 RNA, the geometric mean of the number of copies will be used as opposed to the arithmetic mean • Assessments not chosen for use in summary statistics by this algorithm will still appear in the associated listings. Also, such valid assessments will be used when determining values of potential clinical concern for the 'any time' time point, and for any algorithm that has specific rules for which observation to use (e.g., Snapshot).

Treatment Start Date
 
Treatment start date is defined as follows:
 
 • Maintenance Phase 
 ○ For participants randomized to Q2M: Date of first dose of CAB + RPV (oral or injection) entered in the IP exposure CRF form. ○ For participants randomized to BIK: BIK regimen start date entered in the Maintenance Phase IP exposure CRF • Extension Phase 
 ○ For participants continuing CAB LA + RPV LA (Q2M): 
 - for Q2M OLI: Date of the nominal Month 14 injection date - for Q2M D2I: Date of the nominal Month 13 injection date ○ For participants switching from BIK to Q2M: Date of the nominal Month 13 Q2M injection date (BIK to D2I) or the oral CAB + RPV start date entered in the Extension Phase IP exposure CRF (BIK to OLI)

Study Day
 
The Study Day of an event (e.g., lab assessment, vital sign, ECG, start date of AE or HIV associated/AIDS-defining condition) will be derived as the number of days between the date of the event and the Maintenance Phase start date of study treatment as follows:
 
if date of event ≥ start date of study treatment, then
 
 • Study Day = Date of Event – Start Date of Maintenance Phase IP + 1 
if date of event < start date of study treatment, then
 
 • Study Day = Date of Event – Start Date of Maintenance Phase IP 
Note that the start date of study treatment on Maintenance Phase is considered to be on Study Day 1 and the day before this is Study Day -1; i.e., there is no Study Day 0.

Injection Study Day (Maintenance Phase) (Only applicable to Q2M OLI subjects)

The Injection Study Day of an event will be derived as the number of days between the date of the event and the date of first Maintenance Phase injection as follows:

if date of event \geq first Maintenance Phase injection, then

- Injection Study Day = Date of Event – Date of First Maintenance Phase CAB/RPV Injection + 1

if date of event $<$ first Maintenance Phase injection, then

- Injection Study Day = Date of Event – Date of First Maintenance Phase CAB/RPV Injection

Note that the date of first Maintenance Phase injection is considered to be on Injection Study Day 1 and the day before this is Injection Study Day -1; i.e., there is no Injection Study Day 0.

Extension Study Day

The Extension Phase Study Day of an event (e.g., lab assessment, vital sign, ECG, start date of AE or HIV associated/AIDS-defining condition) will be derived as the number of days between the date of the event and the initial start date of Extension Phase IP as follows:

if date of event \geq start date of Extension Phase IP, then

- Extension Study Day = Date of Event – Start Date of Extension Phase IP + 1

if date of event $<$ start date of Extension Phase IP, then

- Extension Study Day = Date of Event – Start Date of Extension Phase IP

Note that the start date of Extension Phase IP is considered to be on Extension Phase Study Day 1 and the day before this is Extension Phase Study Day -1; i.e., there is no Extension Phase Study Day 0.

Extension Injection Study Day (Only applicable to Extension Switch OLI subjects)

The Extension Phase Injection Study Day of an event (e.g., lab assessment, vital sign, ECG, start date of AE or HIV associated/AIDS-defining condition) will be derived as the number of days between the date of the event and the initial start date of Extension Phase injection as follows:

if date of event \geq date of first Extension Phase injection, then

- Extension Injection Study Day = Date of Event – Date of First Extension Phase CAB/RPV Injection + 1

if date of event $<$ date of first Extension Phase injection, then

- Extension Injection Study Day = Date of Event – Date of First Extension Phase CAB/RPV Injection

Note that the date of first Extension Phase Injection is considered to be on Extension Injection Study Day 1 and the day before this is Extension Injection Study Day -1; i.e., there is no Extension Phase Injection Study Day 0.

Long-Term Follow Up Study Day

The Long-Term Follow Up (LTFU) Study Day of an event (e.g., lab assessment, start date of AE or HIV associated/AIDS-defining condition) will be derived as the number of days between the date of the event and the end of IP treatment [i.e max (Last IM Injection Date, Last Oral Bridging End Date)] as follows:

If the onset of event falls in Long-term Follow up Phase, then

- LTFU Study Day = Date of Event – End Date of IP

16.6.2. Study Population

Demographics and Baseline Characteristics

Age
 
 • Age, in whole years, will be calculated with respect to the participant’s Screening visit. • GSK standard IDSL algorithms will be used for calculating age where birth date will be imputed as follows: • Any participant with a missing date and month will have this imputed as ‘30th June’. • Birth date will be presented in listings as ‘YYYY’. • Completely missing dates of birth will remain as missing, with no imputation applied. Consequently, the age of the participant will not be calculated and will remain missing.

Body Mass Index (BMI)
 
 • BMI is calculated as Weight (kg) / Height (m)². Height is only collected at Baseline Day 1.

Hepatitis Status
 
 • Hepatitis status at entry will be based on the assessments prior to/on the start of the study treatment. • A participant will be considered positive for hepatitis B virus (HBV) if they have a positive surface antigen or detectable HBV DNA result. “HBV DNA DETECTED” in the lab comment takes precedence over HBV DNA test result for positive hepatitis B status, for example, if a participant has HBV test result below level of detection, however, the lab comment shows that HBV DNA detected, this participant will be considered positive for hepatitis B. If HBV DNA result is available, it will be used to qualify hepatitis B status as positive or negative (positive if ≥ limit of quantification); otherwise Hepatitis B status will be determined using the surface antigen result (i.e. “REACTIVE”). • Hepatitis C status will be determined using antibody (IgM or IgG) and/or hepatitis C virus (HCV) RNA assessments performed during screening or during the conduct of the study. If both antibody and virus RNA assessments are available, then the latter will take precedence and positive/negative status will be based on whether HCV RNA is detectable (i.e., ≥ limit of quantification) or not. In the absence of an HBV RNA result, Hepatitis C antibody of “REACTIVE” or “BORDERLINE” will qualify as Hep C positive.

Framingham Risk Equation
 
 • The predicted probability, \hat{p}, of having a cardiovascular disease (CVD) within the next 10-years according to the Framingham formula [D’Agostino, 2008] is 
For females:
 $\hat{p}_F = 1 - S_0(t)^{\exp\{ 2.32888 \times \log(\text{age}) + 1.20904 \times \log(\text{TC}) - 0.70833 \times \log(\text{HDL}) + 2.76157 \times \log(\text{SBP}_u) + 2.82263 \times \log(\text{SBP}_t) + 0.52873 \times I_s + 0.69154 \times I_d - 26.1931\}}$ 
For males:
 $\hat{p}_M = 1 - S_0(t)^{\exp\{ 3.06117 \times \log(\text{age}) + 1.12370 \times \log(\text{TC}) - 0.93263 \times \log(\text{HDL}) + 1.93303 \times \log(\text{SBP}_u) + 1.99881 \times \log(\text{SBP}_t) + 0.65451 \times I_s + 0.57367 \times I_d - 23.9802\}}$

Demographics and Baseline Characteristics

Where

$$S_0(t) = \begin{cases} 0.95012, & \text{females} \\ 0.88936, & \text{males} \end{cases}$$

$$I_s = \begin{cases} 1, & \text{current smoker} \\ 0, & \text{otherwise} \end{cases}$$

$$I_d = \begin{cases} 1, & \text{diabetic} \\ 0, & \text{otherwise} \end{cases}$$

TC = total serum cholesterol (mg/dL),

HDL = serum HDL cholesterol (mg/dL),

SBP_u = systolic blood pressure (mmHg) if participant is not treated for high blood pressure (note that if a participant is treated for high blood pressure then log(SBP_u) = 0)

SBP_t = systolic blood pressure (mmHg) if participant is treated for high blood pressure (note that if a participant is not treated for high blood pressure then log(SBP_t) = 0)

- A participant will be considered as treated for high blood pressure if during screening it has specified that is suffering from hypertension. A participant is classified as diabetic if current or past is indicated in the medical conditions eCRF for Type 1 or Type 2 diabetes mellitus, or if baseline (Day 1) fasting glucose ≥7.00 mmol/L (126 mg/dL) and HbA1C >6.5%.
- Smoking status is collected in the eCRF at Day 1. A current smoker is defined as currently smoking/using tobacco or has smoked/used tobacco within the previous 6 months; a former smoker is defined as previously smoked/used tobacco products and has not smoked/used tobacco products within the previous 6 months.
- This calculation will not be performed for participants who have indicated current or past myocardial infarction conditions on the eCRF. These participants will not be included in summary statistics of risk, but they will be counted in the highest category of risk in the summary by category.
- Framingham Risk will also be calculated at Month 6 and Month 12.
 - Baseline smoking status will be used for the Month 6 calculation. Smoking status collected at Month 12 will be used for the Month 12 calculation.
 - Diabetic status is defined as:
 1. Current or past is indicated in the medical conditions eCRF for Type 1 or Type 2 diabetes mellitus, or
 2. At any time prior to and including the analysis timepoint:
 - 2a. fasting glucose ≥7.00 mmol/L (126 mg/dL) and HbA1C >6.5%, or
 - 2b. an adverse event is collected as having “type 1 or type 2 diabetes mellitus”
 - “Treated for high blood pressure” at Month 6 and Month 12 is defined as
 1. hypertension at baseline or
 2. use of medication treating hypertension which started prior to and including the analysis time point

Lipid-modifying Agents

- The following ATC codes correspond to lipid-modifying agents:
 - ATC Level 2: C10
 - ATC Level 3: C10A, C10B (if Level 2 is not available)

Demographics and Baseline Characteristics

 ○ ATC Level 4: C10AA, C10AB, C10AC, C10AD, C10AX, C10BA, C10BX (if level 2, 3 are not available) ● Participants are considered to have used a lipid-modifying agent at baseline if they are taking the medication at the time of their baseline fasting lipid testing date. ● Participants are also considered to have used a lipid-modifying agent at baseline if they stopped their lipid modifying medication within 12 weeks prior to their baseline fasting lipid testing date.
Treatment Compliance

 ● For defining protocol deviation (i.e. treatment non-compliance) leading to exclusion from the Per Protocol population, the total non-compliance days will be calculated (see details in Section 16.1). The percentage of the total number of non-compliant days to the Exposure ('overall exposure' for CAB+RPV treatment) will be used to define protocol deviation leading to exclusion from PP Population for the Month 12 analysis due to study treatment non-compliance (i.e. >10%).
Adherence to CAB/RPV Injection Schedule

Timeliness of Injections relative to Date of Projected Dosing Visits are assessed by using "actual injection visit date - projected visit date from first injection". The injections of interest in adherence analysis are those after first injection. For participants who choose oral lead-in (Q2M OLI), the first injection is planned at Month 1. For Q2M D2I participants, the first injection is planned at Day 1. Each injection visit is counted only once. Individual CAB and RPV injections administered at the same visit are not counted twice. "Extra" unscheduled injections are excluded from all derivations. For example, if during a scheduled visit a participant receives 2 ml of injection instead of 3 ml due to a dosing error, but this participant returns one week later for the remaining 1 ml injection, then the additional visit is excluded. If a participant receives an extra injection at an unscheduled visit by mistake, this visit will also be excluded.
 
The categories of Timeliness of Injections relative to date of Projected Dosing Visits for summary are listed below:
 
 < -14 days -14 to - 8 days -7 to - 4 days -3 to -2 days -1 day 0 day 1 day 2 to 3 days 4 to 7 days 8 to 14 days >14 days Missed Injection without Oral Bridging Missed Injection with Oral Bridging Missed Injection with CAB+RPV Oral Bridging Missed Injection with SOC Oral Bridging

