16.15.4. Study Population Tables

Note analysis population below has been updated to reflect the M12 analysis plan. In the Month 6 analysis, ITT-E was used prior to this amendment.

Study Population Tables					
No.	Population	GSK Standard / Example Shell	Title	Programming Notes	Deliverable [Priority]
Subject Disposition					
1.1.	Screened	ES6	Summary of Screening Status and Reasons for Screen Failures		M6, M12
1.2.	Enrolled	NS1	Summary of Number of Subjects Enrolled by Country and Site ID	Only include "no treatment" if there is any enrolled but not randomized. Column Header style 2.	M6, M12
1.3.	mITT-E	Shell POP_T1	Summary of Subject Accountability: Study and Phase Conclusion Record	See 207966/primary_15/T1.3 Include the sections: "Outcome of Adverse Events Which Led to Study Withdrawal" (Fatal and Non-Fatal); "Type of Adverse Events Which Led to Study Withdrawal" (COVID-19 and Non-COVID-19)	HL, M6, M12, EOS
1.4.	mITT-E	Shell POP_T4	By Phase Summary of Subject Disposition	201584/primary_07/T1.14	M12, EOS
1.5.	mITT-E	HIV_ES1	Summary of Reasons for Withdrawals by Visit (Maintenance Phase)	201584/ primary_07/T1.9	M6, M12
1.6.	mITT-E	ES1	Summary of Study Drug Discontinuation	mid207966/primary_15/T1.10. Include the sections for fatal/non-fatal, COVID/Non-COVID	M6, M12, EOS

Study Population Tables					
No.	Population	GSK Standard / Example Shell	Title	Programming Notes	Deliverable [Priority]
Protocol Deviation					
1.7.	mITT-E	Shell POP_T2	Summary of Important Protocol Deviations	ICH E3	M6, M12, EOS
1.8.	mITT-E	IE1	Summary of Inclusion/Exclusion Criteria Deviations	Header Style 1	M6, M12
Population Analysed					
1.9.	Screened	Shell POP_T3	Summary of Study Populations		HL, M6, M12, EOS
1.10.	mITT-E	Shell POP_T2	Summary of Protocol Deviations Leading to Exclusion from the Per-Protocol Population - (Month X Analysis)	[X =12 or 6] Add footnote: Month 6 Analysis: Month 6 (OLI and BIK)/Month 5 (D2I) or Month 12 Analysis: Month 12 (OLI and BIK)/Month 11 (D2I)	M6, M12
Demographic and Baseline Characteristics					
1.11.	mITT-E	mid207966/primary_15/T1.16	Summary of Demographic Characteristics		HL, M6, M12
1.12.	Screened	mid207966/primary_15/T1.17	Summary of Age Ranges	Including a column for No treatment	M6, M12
1.13.	mITT-E	DM6	Summary of Race and Racial Combinations Details		M6, M12
1.14.	mITT-E	mid207966/primary_15/T1.20	Summary of Hepatitis Status at Entry		M6, M12
1.15.	mITT-E	CDC1	Summary of CDC Stages of HIV Infection at Maintenance Baseline		M6, M12

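### Hepatitis status at entry: the HCV rule admits on-study results, the HBV sentences disagree for one result pattern, and the HCV fallback names the wrong virus

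*SAP*

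**What the plan says.** The derivation is the Hepatitis Status cell of SAP Section 16.6.2.

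- **Time window.** The opening bullet says "Hepatitis status at entry will be based on the assessments prior to/on the start of the study treatment".
- **HBV.** A participant is positive "if they have a positive surface antigen or detectable HBV DNA result". A laboratory comment that HBV DNA was detected counts as positive even when the numeric result is below the limit. The bullet then ends: "If HBV DNA result is available, it will be used to qualify hepatitis B status as positive or negative". The cut is at the limit of quantification, and surface antigen is used only when there is no DNA result.
- **HCV.** The tests that count include "hepatitis C virus (HCV) RNA assessments performed during screening or during the conduct of the study", alongside antibody. Where a participant has both kinds of result, RNA prevails over antibody, and no date limit is attached. The fallback begins "In the absence of an HBV RNA result, Hepatitis C antibody", and a reactive or borderline antibody then counts as positive.

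The only planned summary of this variable is Table 1.14, "Summary of Hepatitis Status at Entry" (Section 16.15.4), on the mITT-E population, delivered at Month 6 and Month 12. It is also listed in Table 1 of Section 6.1.

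**The concern.** A status labelled as at entry should depend only on data up to first dose. The HCV bullet sets a wider window than the bullet that introduces the cell, and its precedence rule has no date limit. An HCV infection acquired on study could be tabulated as present at entry, and a later negative RNA could remove a participant who counted as positive on entry data. Because Table 1.14 is produced at two data cuts, a participant's entry status could also differ between them.

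The HBV bullet contains two rules that are not equivalent, so two programmers could each follow the text and classify the same participant differently. The fallback that names HBV RNA inside the hepatitis C bullet is a further error in the same cell.

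What is at stake is the accuracy and reproducibility of one baseline table.

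**Working it through.** The plan gives no figure to reproduce. The check applies the rules of Section 16.6.2 to every combination of test results.

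**HBV.** Inputs: surface antigen (reactive or not) and four DNA states (no result; below quantification; below quantification with the comment that DNA was detected; at or above quantification), so 2 × 4 = 8 patterns. Rule A is the first sentence: either test suffices. Rule B is the last sentence: DNA decides if available, otherwise antigen. The comment makes the participant positive under both. Detectable is taken as at or above quantification or flagged by the comment; the HCV bullet itself equates detectable RNA with that limit.

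| Surface antigen | HBV DNA | Rule A | Rule B |
|---|---|---|---|
| Reactive | none | positive | positive |
| Reactive | below limit, no comment | **positive** | **negative** |
| Reactive | below limit, comment | positive | positive |
| Reactive | at or above limit | positive | positive |
| Non-reactive | none | negative | negative |
| Non-reactive | below limit, no comment | negative | negative |
| Non-reactive | below limit, comment | positive | positive |
| Non-reactive | at or above limit | positive | positive |

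The rules disagree in 1 of 8 patterns, and there rule B turns a positive into a negative.

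**HCV.** Inputs: antibody (2 states), entry RNA (none, positive, negative) and on-study RNA (same 3 states), so 2 × 3 × 3 = 18 patterns. The entry-only window was compared with the wider window of the HCV bullet, with RNA over antibody in both. Six patterns are affected.

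| Antibody | Entry RNA | On-study RNA | Entry data only | HCV bullet |
|---|---|---|---|---|
| Reactive | none | negative | positive | negative |
| Non-reactive | none | positive | negative | positive |
| Reactive | positive | negative | positive | undefined |
| Reactive | negative | positive | negative | undefined |
| Non-reactive | positive | negative | positive | undefined |
| Non-reactive | negative | positive | negative | undefined |

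Two patterns change outright, one in each direction. In the other four the plan does not say which RNA result applies.

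**How often on-study results could arise.** The Maintenance Phase schedules for OLI, D2I and BIK (Section 16.2) mark hepatitis testing at Screening only. That row lists hepatitis B serology and HCV antibody; neither HBV DNA nor HCV RNA is named. An on-study HCV RNA result would therefore have to come from an unscheduled test.

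**Where the variable is used.** Hepatitis status is not a randomisation stratum or a listed subgroup (Section 5.4), nor a covariate in the models set out in Sections 8.4, 8.5 and 13.5. It feeds Table 1.14.

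**The case against.** The best defence is that the opening bullet governs the whole cell, so the HCV bullet is implicitly limited to entry samples and Table 1.14 is safe. That reading is natural, but the text does not state it, and it leaves the reference to on-study tests with no purpose, since no other hepatitis summary is planned. The contradiction stands.

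For HBV, the last sentence can be read as the operative hierarchy and the first as a general introduction. That is also fair, but the first sentence makes a reactive antigen sufficient without qualification, so the plan should say which one applies.

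On the fallback, the sentence just before it already gives HCV RNA precedence when both tests exist. A reader might infer that the plan never checks whether HCV RNA is available; that goes too far. This is an evident slip that a careful programmer would probably read correctly.

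The objection that practical impact is small stands in full.

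**Conclusion.** The HCV window contradicts the entry window as written and can put results obtained after first dose into a baseline table, in either direction. The HBV conflict is real but narrow: one pattern, one direction. The fallback is a wrong-virus slip. The consequence is limited to descriptive Table 1.14 and is probably small, given testing scheduled at Screening only. No efficacy result, modelled result or analysis population changes.

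Four stronger readings are tempting, and the document does not support them.

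- **Every surface-antigen-reactive participant is both positive and negative.** Three of the four reactive patterns are positive under both rules, and the laboratory comment resolves some results below the limit.
- **A number of misclassified participants.** One could apply an assumed HCV incidence to the approximately 654 participants planned. The SAP gives no incidence, and the sum would also require each new infection to be tested and recorded on study despite no scheduled test.
- **Damage to the hepatic safety analyses.** The SAP does not link Table 1.14 to the hepatic events of special interest or to the liver displays.
- **Special importance because participants enter on a regimen containing FTC and TAF.** The SAP says nothing about that regimen and hepatitis B. Whether antigen-reactive people could enrol depends on eligibility criteria that are not shown here; if they could not, the HBV conflict may affect no one.

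**What to change.** In Section 16.6.2:

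1. In the HCV bullet, delete the clause that extends "assessments performed during screening or during the conduct of the study" beyond screening, and state that only samples dated on or before first dose determine entry status.
2. Reconcile the two HBV sentences into one stated hierarchy that explicitly covers a reactive surface antigen with DNA below quantification and no comment of detection. Which classification to adopt is for the sponsor to decide and state; the document does not settle it.
3. Replace HBV RNA with HCV RNA in the antibody fallback.

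The cost is three wording edits and a re-derivation of one baseline variable for Table 1.14. No new data are needed.
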